#### 3.8 Safety and Other Outcome Measures Analyses

All safety analyses will be done for the Safety population unless noted otherwise.

#### 3.8.1 Treatment Exposure

Based on the Procedure CRF data as follows, number and percentage of subjects with VeraCept successfully placed will be presented for ITT and Safety populations.

- Was device deployed (at first try)? (Yes, No)
- If No, will a second attempt be made? (Yes today, Yes another visit, No)
- Was device deployed at second attempt? (Yes, No)

VeraCept successfully placed

Furthermore, number of cycles (28 days = 1 cycle) with VeraCept use will be summarized by the 6-number statistics for Safety population.

An overall AE high-level summary table will also be provided for both ITT and Safety populations with total number and percentage of distinct subjects (but no SOC or PT) for:

- AE onset time frame (By Day 42/Week 6, From Day 43 through Day 91/Week 13, From Day 92 through Day 182/Week 26, Day 183 and later)
- AE severity (Mild, Moderate, Severe)
- AE relatedness (Not Related, Unlikely Related, Probably Related, Related)
- Related AEs (including Unlikely Related, Probably Related, Related) onset time by cycle (Cycle 1 through Cycle 13).
- SAE
- Discontinued study due to any AE
- Death due to any SAE.

Another high-level summary table for both ITT and Safety populations will present the counts of events (not distinct subjects) as following chart. Note that each percentage, if provided, is based on the number on the one where "(100.0)" is displayed. This AE summary table provides the cross reference between every level of relatedness and severity.

	AE Severity							
Relatedness				Total # (%) of				
	Mild	Moderate	Severe	Events				
Not Related	XX	XX	XX	xx (x.x)				
Unlikely Related	XX	XX	XX	xx (x.x)				
Probably Related	XX	XX	XX	xx (x.x)				
Related	XX	XX	XX	xx (x.x)				
Total # (%) of Events	xx (%)	xx (%)	xx (%)	xx (100.0)				

Two listing-style tables, one is for SAEs, and the other is for AEs that led to premature study discontinuation, will also be presented, with the details about the event onset date, resolved date, days of onset since the VeraCept placement, severity, outcome, treatment for the AE, and relatedness to the study device, as well as other supportive data such as the subject's age and number of days on study.

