12.3.1 Monthly Phone Contact (up to 52 Weeks)

Subjects will be contacted by phone each month, after her menses, to confirm completion of the monthly diary for:

- The need for additional contraception;
- Use of concomitant contraception;
- Use of concomitant medications;
- Documentation of menstrual and intermenstrual bleeding;
- Assess if there have been any adverse events since the last contact; and
- Resolution of any prior serious adverse events or adverse events.

12.4 Long-term Follow-up post 52-week visit (Every 6 Months: Months 18-30 (±4wks) and 3 yrs (-3wks/+4wks) /Exit visit

The subject will return for follow up after their Week 52 visit, every 6 months, if they choose to continue with the study visit. During these visits, the subject will be evaluated for:

- Vital signs and weight
- General physical exam (same as at Screening Visit)
- Pelvic exam (string check)
- Transvaginal ultrasound to document VeraCept position (only if indicated)
- Pregnancy test, urine
- Interval and concurrent medications
- Adverse events
- Verify sexual activity

Document any back-up contraception methods

Additionally, at the final visit at 3 Years / Exit visit, the following will also be performed:

- Transvaginal ultrasound to document VeraCept position
- VeraCept Removal
- Urine pregnancy test will be done 17 days after removal/study exit by the subject at home, with a follow up call by the study coordinator or PI required to document results.

A 2-week supply of hormonal contraceptive pills will be provided to the subject by the site as a contraceptive option for the first two weeks after VeraCept removal.

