#### 2.3 Trial Design

This is a prospective, multi-center, single-arm, open-label, Phase II clinical study. Each subject will be followed for 12 months after device placement for the protocol endpoints, and then every 6 months thereafter for those subjects who wish to continue study device use up to a maximum of 3 years.

Physical assessment (office visit) will occur at Weeks 6, 13, 26 and 52 after placement, with monthly telephone contact. For those subjects who wish to continue study device use after 12 months (up to 2 additional years for a total maximum of 3 years), follow-up office visits will occur every 6 months, and also contacted by phone calls, e-mail or text

message every 28 days (Cycle Contact). Additional visits will be conducted if necessary for safety issues.

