## 3.1.3 Analysis Conventions

This section details general policies to be used for the statistical analyses. Departures from these general policies may be given in the specific detailed sections of this statistical analysis plan. When this situation occurs, the rules set forth in the specific section take precedence over the general policies. The following policies will be applied to all data presentations and analyses.

- Summary statistics will consist of the number and percentage of responses in each category for discrete (categorical) variables, and the number of non-missing observations (n), mean, median, standard deviation (SD), minimum, and maximum (abbreviated as 6-number summary statistics) for continuous variables.
- All mean values will be formatted to one more decimal places than the measured value, and standard deviation values will be formatted to two more decimal places than the measured value. For median values, they will be kept the same decimal place as the measured values if that is doable without losing accuracy; otherwise, they will be formatted to one more decimal place than the measured values.
- All percentages will be rounded to one decimal place. The number and percentage
  of categorical responses will be presented in the form XX (XX.X), where the
  percentage is in the parentheses. The denominator for percentage calculations will
  be either the number of non-missing observations (n) when this number is shown, or
  the total sample size of the relevant sample size for tables of adverse events, medical
  histories, or other tables where this number of non-missing observations (n) is not
  presented.
- All listings will be sorted for presentation in the order of site identifier, subject identifier, and date of procedure or event.
- When necessary for analysis purposes, partial dates will be completed (i.e., turned into complete dates) using the most conservative approach.
- All analysis and summary tables will have the population sample size in the column heading.
- Baseline is defined as the last data point before the placement of study product.
- Calculating change from baseline to a visit will be done as follows: Change from Baseline = Observed value at the visit – Baseline value.
- Subjects who have only baseline (without any post-baseline measurements) for a
  parameter at a visit, or only have post-baseline value for a parameter at a visit, will be

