- EP subjects never had live birth

Life-Table (Kaplan-Meier) method will also be used to present probabilities of pregnancy-free through Year 1 (Day 365), Year 2 (Day 730), and Year 3 (Day 1095 + 2 weeks, or Study Day 1109). If a subject doesn't have an on-treatment pregnancy, the event time will be censored at that day (of study device removal, or day of last contact).

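### The last AE onset window (Day 183 onward) has no upper limit, so in the 3-year analysis its percentage cannot be compared with the earlier windows as a time trend

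*SAP*

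**What the plan says.** SAP 3.8.2 plans an overall AE summary for the Safety and ITT populations (Tables 14.3.1.1 and 14.3.1.1T in SAP 5.2), "with total number and percentage of distinct subjects (but no SOC or PT) for" several blocks. One block is onset time: "AE onset time frame (By Day 42/Week 6, From Day 43 through Day 91/Week 13", followed by "From Day 92 through Day 182/Week 26, Day 183 and later". No end is given for the fourth window.

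SAP 3.1.3 sets the percentage base as "the total sample size of the relevant sample size for tables of adverse events", which is the full population and not the women still under follow-up in a window. SAP 3.8.2 gives no person-time for these rows.

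SAP 3.1.2 says the end-of-study analysis takes in all 3-year data. Under SAP 2.3, women who wish to continue may do so for "up to 2 additional years for a total maximum of 3 years". The long-term visit schedule (title of Protocol 12.4, and Table 1) is "Months 18-30 (±4wks) and 3 yrs (-3wks/+4wks) /Exit visit".

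AE enquiry is closer in Year 1 than later. Protocol 15 has women record AEs in the daily diary. The monthly call to Week 52 (Protocol 12.3.1) includes "Assess if there have been any adverse events since the last contact". After Week 52, Table 1 shows no diary collection. The 28-day contact in Protocol 12.4.1 covers only sexual activity and back-up contraception, and AEs are next asked about at the 6-monthly visits (Protocol 12.4).

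**The concern.** The four rows will be printed one under another as percentages of the same N, and a reader will compare them. Three things other than AE risk differ between the fourth row and the rest: the length of the window, the women who can contribute to it, and how AEs are found. Length pushes the fourth percentage up, while attrition and sparser enquiry push it down. The net effect cannot be read from the table.

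A flat or moderately falling AE rate could then look like a late rise in a summary meant to support Phase III planning. AEs starting in Days 183 to 364 also cannot be told apart from extension AEs in this table.

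A likely origin, though this is inference, is that the windows were carried over from the Year 1 SAP on which this one is built (SAP 1.0). On 1-year data the open window would have ended near Week 52 without needing to say so.

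**Working it through.** **Reproducing the plan's cut-points.** Days = weeks × 7: 6 × 7 = 42, 13 × 7 = 91, 26 × 7 = 182. These match the SAP. Week 52 is Day 364.

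**Window lengths** (last day − first day + 1):
- Days 1 to 42: 42 days
- Days 43 to 91: 49 days
- Days 92 to 182: 91 days
- Day 183 to Day 1095: 913 days
- Day 183 to Day 1109, the Kaplan-Meier cut-off in SAP 3.7.2 ("Year 3 (Day 1095 + 2 weeks, or Study Day 1109"): 927 days
- Day 183 to Day 1123 (1095 + 28, the end of the 3-year visit window): 941 days
- Day 183 to Day 364, if closed at Week 52: 182 days

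At its longest the fourth window is 941/42 = 22.4 times the first. Closed at Day 364 it is 182/42 = 4.3 times. Of the 941 days, 941 − 182 = 759 (81%) fall after the diary and monthly calls have ended.

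**Illustration at a constant rate.** The documents give neither an AE rate nor a continuation share, so both are assumed. With rate r per woman-year, the chance of at least one AE in d days is 1 − exp(−r × d/365.25).

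For r = 1:
- 42 days: 10.9%
- 49 days: 12.6%
- 91 days: 22.1%
- 182 days: 39.2%
- 913 days: 91.8%

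If a share c continues to Day 1095 and the rest stop at Day 364, the fourth row is c × 91.8% + (1 − c) × 39.2%:
- c = 0.5: 65.5%
- c = 0.7: 76.0%

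For other rates, with c = 0.5 and follow-up to Day 1123, the fourth row is 47.2% at r = 0.5 and 81.3% at r = 2. The third row at those rates is 11.7% and 39.2%.

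**Falling rate** (r = 1 to Day 182, c = 0.5, end at Day 1095):
- Rate halves after Day 182: 0.5 × [1 − exp(−0.5 × 913/365.25)] + 0.5 × [1 − exp(−0.5 × 182/365.25)] = 46.7%.
- The same, with only half of the AEs after Week 52 captured. Effective days for continuers are 182 + 0.5 × 731 = 547.5, and the row is 37.4%.
- Rate falls by 75%, half captured: 21.5%.

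So the fourth row still stands above the third (22.1%) when the rate is halved and half of the later AEs are missed. Only a more extreme fall removes the apparent rise.

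**What the early rows can still show.** If the rate is 2 in Days 1 to 42 and 1 afterwards, the first two rows read 20.5% and 12.6%, against 10.9% and 12.6% under a flat rate. An early excess stays visible.

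**Effect of closing the window alone.** A flat rate would read 10.9%, 12.6%, 22.1% and 39.2%, still rising because the lengths are unequal.

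**The case against.** The case against giving this much weight is substantial, and most of it stands.

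- A reader might infer that the whole onset pattern is an artefact. The documents do not support that. The first three windows lie inside the diary and monthly-call period, and the first two are nearly equal in length. The fourth row is the one badly affected.
- A reader might infer that the table cannot show whether AEs settle after insertion. The same table also gives related AEs (including those rated unlikely related) by 28-day cycle for Cycles 1 to 13. These are equal intervals through Day 364.
- A reader might take this as a failure to answer the tolerability question. Protocol 5.2 and SAP 2.4.2 define tolerability by bleeding and spotting patterns and discontinuation. SAP 3.8.5 summarises bleeding by cycle, and SAP 3.8.4 does the same for cramping and pelvic pain.
- The table is descriptive. No test or formal comparison across windows is planned, and SAP 3.1.2 makes the 1-year analysis the main one.
- The figure of about 940 days is a maximum. For a woman who leaves at Week 52 the last window is 182 days, or 196 at the end of that visit window.
- The illustration assumes that every woman reaches Day 364, and in its main form that detection is equal throughout. Both raise the fourth row.

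What does not stand is that the other displays fill the gap. The cycle row omits unrelated AEs and stops at Cycle 13. The yearly tables in SAP 3.8.2 are by preferred term, state no exposure or at-risk denominator, and do not isolate Days 183 to 364. As written, Year 3 starts at Day 371 and so overlaps Year 2 (Days 366 to 730). The AE listing holds the dates but is not a summary.

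**Conclusion.** The point holds for the fourth row only. An open window of up to 913 to 941 days, with full-population percentages and no person-time, cannot be compared with windows of 42, 49 and 91 days. It also mixes two levels of AE enquiry and two sets of women. No planned summary table separates all AEs with onset in Days 183 to 364 from extension AEs.

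In size, the fourth row would read about 65% to 76% instead of 39.2% under a flat rate of 1 AE per woman-year. That rests on an assumed rate, assumed continuation of 50% to 70%, equal detection, and all women reaching Day 364. The direction survives a halved rate with half of the later AEs missed. The window lengths and the change in AE enquiry rest on the documents alone.

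It does not follow that the early onset pattern is unreadable, that the Year 1 analysis is affected, or that a planned inference fails. This is a low-severity improvement to a descriptive table.

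**What to change.** In SAP 3.8.2, for Tables 14.3.1.1 and 14.3.1.1T:

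1. Close the fourth window at Day 364 (Days 183 to 364).
2. Show extension onset in separate Year 2 and Year 3 windows, with women still using the device at the start of each as the denominator.
3. Add woman-years and events per 100 woman-years for every window, including the first four. Closing the window alone leaves unequal lengths.
4. Add a footnote that scheduled AE enquiry became less frequent after Week 52, when the diary and monthly calls ended.
5. Reconcile the yearly boundaries while doing this. The stated Year 3 start (Day 371) overlaps Year 2. Year 1 ends at Day 365 in the yearly AE tables but at Day 364 in the proposed window, so each day needs exactly one home. State also where onsets after Day 1095 go, since the exit visit may fall up to 4 weeks later.

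The cost is SAP wording and some extra rows and columns in two tables, from onset, placement and exit dates already collected. The downside is slightly larger descriptive tables.

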15.3 Causality: Serious Adverse Event and Adverse Event Relationship to Study Treatment

The Investigator will assess the relationship of the SAE and AE to study device placement procedure (procedure) or study device by using the following general guidelines:

Not Related: A causal relationship between the study device and the AE can be ruled out (e.g., based on the temporal sequence, absence of a reasonable pathophysiological mechanism, or direct evidence of actual cause).

Unlikely related: A clinical event, including laboratory test abnormality, with a temporal relationship to procedure or study device initiation which makes a causal relationship improbable, and in which other drugs, chemicals or underlying disease provide plausible explanations.

Probably Related: A clinical event, including laboratory test abnormality, with a reasonable time sequence to first attempt of study device placement, unlikely to be explained by concurrent disease or other drugs or chemicals. Information on drug withdrawal may be lacking or unclear.

Related: A clinical event, including laboratory test abnormality, with a reasonable time sequence to first attempt of study device placement, cannot be attributed to concurrent disease or other medical devices, drugs, or chemicals, and which follows a clinically reasonable response on withdrawal.

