## 1.0 INTRODUCTION

This statistical analysis plan (SAP) was developed based on the Version 1.00 SAP for Year 1 data analysis, after reviewing the Sebela Pharmaceuticals Development LLC (Sebela) CMDOC-0008 study protocol (Version 5.0, dated as 29SEP2017) and electronic case report forms (eCRFs, dated as 30JAN2018), but before final analysis of the Year 2 and Year 3 data analysis had begun. Detailed information is given to aid in the production of the statistical outputs and the statistical section of Final Clinical Study Report (CSR). This document gives a summary of the protocol and describes the populations that will be analyzed. All subject characteristics and the efficacy and safety parameters that will be evaluated, along with the specific statistical methods, are described.

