## 2.4 Study Endpoints

## 2.4.1 Primary Endpoints

The primary outcome measure is study device effectiveness, evaluated as the absence of pregnancy up to 12 months (13 cycles of 28 days each) of VeraCept use.

Contraceptive failure rate will be calculated using the Pearl Index through 13 cycles. All evaluable cycles prior to discontinuation or planned removal at 12 months (13 cycles) will be included in the primary analysis of effectiveness. The calculation will be first done for all ("Total") subjects, and then for sub-groups of parous ("Parous") and nulliparous ("Nulliparous") women of child-bearing age.

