## 3.1.2 Analysis of 1-Year data

An analysis of the 1-year data was performed after all the subjects are enrolled and all the 1-year data were collected, monitored, and cleaned. All outputs in Section 5.2 that involve 1-year data were created since this analysis was the final analysis of the 1-year data. The analysis of 1-year data was the main analysis for the study. Secondarily, an analysis will be done at the end of the study to include all 3-year data.

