## 3.7.2 Efficacy Analyses for the Whole Study

Post-Year 1 sexual activity and contraceptive use information can be found in the Cycle Contact CRF, which was added since the Extension study (Year 2) started, i.e., this CRF wasn't present from the beginning of the study, but added as a mid-study change. Each record in this form is for one cycle and has the following 2 key questions for determining if a cycle is pregnancy-risk or not:

- Did the subject have intercourse at least once during the cycle? (Yes, No)
- Did the subject use backup contraception during the cycle? (Yes, No)

If the answer is "Yes" to the first question and "No" to the second question, or the subject was pregnant within a cycle (determined form the Pregnancy Test form), that cycle will be considered as a pregnancy-risk cycle; otherwise, the cycle will not be considered as a pregnancy-risk cycle.

For cycles without any Cycle Contact information, e.g., neither of the above 2 "Yes"/"No" questions were answered and a subject wasn't pregnant within the cycle either, the following procedure will be used to do the estimate for the subject:

- A. find the total number of such type of cycles for that subject
- B. find proportion of pregnancy-risk cycles from Year 1 diary data of the subject, which will be calculated as the number of pregnancy-risk cycles divided by the total number of cycles from Diary CRF
- C. The number from Step A is multiplied by the number from Step B, and then rounded to 1 decimal place, which will be the estimated number of pregnancy-risk cycles where Cycle Contact information is missing for the subject.

The number from Step C will be added to the number of pregnancy-risk cycles from those without missing Cycle Contact information, and then added to the Year 1 pregnancy-risk cycles from Diary CRF data to get denominator value of the Pearl Index for Year 2 (data cut off at 26 cycles) and Year 3 (data cut off at 39 cycles). The numerator will be the number of on-treatment pregnancies by the end of Cycle 26 and Cycle 39, respectively.

The Year 2 and Year 3 analyses will also be performed without inclusion of cycles with missing Cycle Contact information, i.e., not doing estimates of pregnancy-risk through the above Steps A, B, and C.

The 95% Confidence Intervals for the Pearl Index will be calculated, by using the formula in the above Section 3.7.1, at the following 3 scenarios:

- All EP subjects
- EP subjects with at least one live birth

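### The by-cycle Related AEs row pools Unlikely Related events and stops at Cycle 13, so no summary table shows when Probably Related or Related AEs begin

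*SAP*

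**What the plan says.** SAP 3.8.2 plans an overall AE table for the ITT and Safety populations that counts distinct subjects (Tables 14.3.1.1 and 14.3.1.1T). One of its rows reads "Related AEs (including Unlikely Related, Probably Related, Related) onset time by cycle (Cycle 1 through Cycle 13".

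Protocol 15.3 has four causality grades: Not Related, Unlikely related, Probably Related and Related. For Unlikely related, it describes an event with a timing "which makes a causal relationship improbable, and in which other drugs, chemicals or underlying disease provide plausible explanations". Not Related is kept for events where causality can be ruled out.

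The SAP covers the full study. Section 1.0 says that it was prepared from the Year 1 SAP, "but before final analysis of the Year 2 and Year 3 data analysis had begun". Section 3.1.2 adds: "Secondarily, an analysis will be done at the end of the study to include all 3-year data". Section 2.3 describes follow-up of women "who wish to continue study device use up to a maximum of 3 years", and Section 3.7.2 sets efficacy limits at "Year 2 (data cut off at 26 cycles) and Year 3 (data cut off at 39 cycles".

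**The concern.** Two features of the row limit its use.

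- **The pooling.** A row headed Related AEs includes a grade that the protocol ties to improbable causality. A reader who wants the onset pattern of events that investigators thought probably or definitely due to the device cannot take it from this row.
- **The end point.** The row has no cell for an event with onset after Cycle 13, although this SAP governs the 3-year report.

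What is at stake is a plain tolerability question for a device worn for up to three years: do related events fade after placement, or do they continue among women who keep the device? The planned summary tables do not answer it.

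**Working it through.** **1. Cycle count.** SAP 2.4.1 equates Year 1 with "12 months (13 cycles of 28 days each", so 13 × 28 = 364 days, which matches the Day 364 limit in SAP 3.7.1. The 3-year limit is 39 cycles, so 39 × 28 = 1,092 days. The row covers 13/39 = 33.3% of the possible cycles. The other 26/39 = 66.7% have no by-cycle cell.

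**2. Does another output supply the timing?**

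| Planned output | Causality shown? | Onset time shown? |
|---|---|---|
| Four-grade relatedness row, same table | Yes | No |
| Relatedness by severity, event counts (14.3.1.2, 14.3.1.2T) | Yes | No |
| SOC/PT by relatedness (14.3.1.8C, 14.3.1.8) | Yes | No |
| Onset bands, same table | No | Yes, but the last band is open from Day 183 |
| Year 1, 2 and 3 AEs by preferred term (14.3.1.3P-Y1 to -Y3) | No | Yes, by year |
| Dyspareunia and allergy-related symptoms by onset year | No | Yes, by year, these terms only |
| List tables of SAEs and of AEs leading to discontinuation (14.3.2.1, 14.3.2.2) | Yes | Yes, subject by subject, these events only |
| AE listing (16.2.7.1) | Not a summary | Not a summary |

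Apart from the by-cycle row, only the two list tables pair causality with onset. A non-serious related AE that did not lead to discontinuation has no summarised timing after Cycle 13. In Cycles 1–13 its timing appears only mixed with Unlikely Related events.

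**3. Can the Unlikely events be subtracted?** No. The four-grade row is a study-wide count of distinct subjects with no time axis, so it cannot be used to remove Unlikely-only subjects from a given cycle.

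**4. Direction and size of the pooling effect.** Let u be the share of subjects in a cycle's cell whose only qualifying event is Unlikely Related. The pooled count is then 1/(1 − u) times the Probably-plus-Related count. The documents give no value for u, so these values are assumptions:

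| u (assumed) | Ratio |
|---|---|
| 0% | 1.00 |
| 10% | 1.11 |
| 25% | 1.33 |
| 50% | 2.0 |
| 75% | 4.0 |

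The pooled count can equal or exceed the narrower one and cannot fall below it. Beyond that, the documents fix nothing.

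**5. Denominator.** SAP 3.1.3 bases AE-table percentages on the total sample size when no count of non-missing observations is shown. If a proportion r of current users has a related AE in a period and a fraction f of subjects still use the device, the table shows about r × f. The percentage would then fall as women stop, even with r constant. Later periods therefore need the number still using the device.

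**The case against.** The case on the other side is substantial, and much of it stands.

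- A reader might infer that **related events in Years 2 and 3 disappear from the report**. They do not. The overall relatedness tables and the AE listings carry no Year 1 limit. Only the by-cycle timing stops.
- A reader might infer that **the row overstates early device toxicity**. The documents do not show this. The pooling applies to every cycle displayed, no counts by causality are given, and the protocol's list of common AEs (Section 6.2) does not say how they were graded.
- A reader might see **a flat contradiction of the protocol**. Protocol 15.3 sets no related/unrelated cut. Since Not Related means that causality is ruled out, the pooled row can be read as every event for which it was not. That is a cautious safety choice, and the row label discloses it. The label is still awkward, and the narrower pattern is still not shown.
- **The 66.7% is a share of cycle labels**, not of exposure or events. Continuing after 12 months is optional, and the documents do not say how many women did.
- **Per-cycle rows to Cycle 39 could suggest precision that the data lack.** Monthly phone contact, which asks about AEs, ends at 52 weeks (protocol 12.3.1). Later cycle contacts cover only intercourse and back-up contraception (12.4.1), and scheduled AE review becomes 6-monthly (12.4). This is a good reason not to extend the row cycle by cycle. It is no reason to show nothing, since blocks of 13 cycles suit 6-monthly review.
- **Later timing is partly covered** by the yearly AE tables, the two terms tabulated by onset year, and the cumulative safety-related removal and expulsion rates. None of these is split by causality grade.

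**Conclusion.** The point holds as a reporting gap of minor severity. The row pools a grade defined as causally improbable with the two higher grades, and it ends at Cycle 13 of 39. As a result, no summary table gives the onset timing of Probably Related or Related AEs in any year, or of related AEs on any definition after Cycle 13. The exceptions are the two subject-level list tables.

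The size of any excess from pooling is unknown; the ratios above rest wholly on assumed values of u. The output is descriptive, in an exploratory single-arm study whose main analysis is at one year. The primary effectiveness analysis is not affected.

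The conclusion rests on the SAP's text and list of outputs. The table shells are a separate document and were not available.

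**What to change.** 1. Add a by-cycle row defined as Probably Related plus Related.
2. Keep the pooled row for continuity with the Year 1 output, but relabel it, for example as causality not ruled out.
3. For both rows, keep Cycles 1–13 individually and add blocks for Cycles 14–26 and 27–39. A Year 1/2/3 split by relatedness would also serve. If it is used, set non-overlapping windows: in SAP 3.8.2 the Year 3 AE table starts at Day 371 while the Year 2 table runs to Day 730.
4. Show the number of subjects still using the device at the start of each cycle or block, and use it as the denominator.

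Per-cycle rows after Cycle 13 are not needed. AE onset and causality are already collected, so the cost is a change of SAP wording and a slightly longer table.
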